5.3 Analysis Populations

5.3.1 Efficacy populations

The analyses of immunogenicity and efficacy endpoints will be performed by the treatment allocation and based on the modified intention-to-treat and per-protocol populations described below.

Modified intention-to-treat (mITT) population: all randomized subjects who receive at least one dose of the study drug and have both baseline and at least one post-baseline assessment in any of the primary or secondary variables, irrespective of compliance with the study protocol and procedures.

Per-protocol (PP) population: subjects who receive all planned doses of the study drug, complete the treatment period, fulfil all entry criteria, and have no key protocol deviation.

5.3.2 Safety population

The safety population is the total treated population defined as all subjects randomized and exposed to at least one dose of the study drug, regardless of the amount of treatment administered.

Safety endpoints and tolerability will be analyzed based on the safety population.

The total number of subjects for each of the following categories will be presented in the clinical study report (CSR).

- Screened subjects: all patients who have signed the inform consent
- Randomized subjects: subjects who receive a randomization number via IVRS/IWRS
- The safety population
- The mITT population
- The PP population

For the following two categories of subjects, counts, and percentages will be calculated for each treatment group using the number of randomized subjects in each group as denominator.

- Subjects who have completed the 60-week treatment period
- Subjects who discontinue the study drug during the treatment period

A list of subjects prematurely withdrawn from the study, along with reasons for discontinuation, will be provided.

5.3.3 Subgroups

While this study is not powered for subgroup analyses, select efficacy and safety endpoints will be analyzed by APOE4 carrier subgroups for exploratory purpose.

5.4 Protocol Deviation Reporting

There is a listing for describing the subjects with protocol violation. It will record the details of the

protocol deviation and its severity level.

5.5 Patient Disposition

The number and percentage of screened patients and screened-failure patient will be summarized for all subjects.

The number and percentage of patients who completed the study and who discontinued the study will be summarized by treatment for all subjects. Discontinuations will be further summarized by reason.

The number and percentage of patients in each analysis sets will be summarized by treatment.

5.6 Enrollment by Site

The number and percentage of patients in each study site will be summarized by treatment in mITT, PP and Safety population.

5.7 Subject Demographics and Baseline Characteristics

5.7.1 Subject Demographic Characteristics, Medical History and Diagnoses

The baseline value is defined as the last available value before the first injection of study drug.

Descriptive statistics will be used to summarize the demographic, baseline characteristics data and medical history for the safety population to describe the study population by study center, treatment group and overall.

The distribution of demographic and baseline characteristics among three treatment groups will be evaluated using chi-square or Fisher's exact test for categorical variables and the Kruskal-Wallis test or analysis of variance (ANOVA) for continuous variables.

Pathologies associated with past medical and surgical history will be classified into primary system organ classes and preferred terms using MedDRA 21.0 and will be summarized by study center, treatment group and overall using counts and percentages. The primary system organ classes and preferred terms will be sorted in decreasing order of frequency.

5.7.2 Physical Examination

The number and percentage of abnormality at baseline will be summarized by treatment in Safety population.

Shift from baseline for post treatment at scheduled visit will be summarized by treatment in safety population with number and percentage.

5.7.3 Medical History and Surgery History

Previous/concomitant medical history and surgery history at baseline will be summarized for safety population by treatment with number and percent of patients by primary system organ class and preferred term.

5.7.4 Previous and Concomitant Medications/Therapy

Medications will be classified into the following two groups:

- Previous medications are those that the subject took within 3 months period prior to the first screening visit (S1) and prior to the first administration of the study drug at Week 0

(V1/baseline).

- Concomitant medications are those that the subject continued or started on or after the first injection of the study drug up to the end of the study.

These medications will be classified into anatomic and therapeutic classes using the World Health Organization (WHO) Drug Dictionary. Subject will only be counted once within each anatomic and therapeutic class.

Descriptive statistics including number of subjects and percentage will be provided. No statistical testing for between-group difference will be performed.

5.7.5 Baseline Efficacy and Safety Data

For efficacy and safety analysis, the baseline for a given parameter is defined as the last available value prior to the first injection of the study medication. Baseline efficacy and safety variables will be summarized by treatment group, and overall.

5.8 Treatment Tolerability and Compliance

Overall treatment tolerability and compliance will be summarized in safety population.

The overall treatment tolerability of UB-311 for each arm is defined as the percentage of number of administered doses divided by number of administered doses plus number of missed doses of subject(s) who drops out due to drug-related AE(s). It is calculated according to the following formula:

$$100\% \times (A+B1+C+D) / (A+B1+B2+C+D)$$

where

A: number of administered doses of completers

B1: number of administered doses of subject(s) who drops out due to drug-related AE(s)

B2: number of missed doses of subject(s) who drops out due to drug-related AE(s)

C: number of administered doses of subject(s) who drops out due to drug-unrelated AE(s)

D: number of administered doses of subject(s) who drops out not due to AE(s)

The overall compliance is defined as the actual dose (UB-311 or placebo) of injection compared to the prescribed dose of treatment during the study. It is calculated according to the following formula:

$$100\% \times (\text{Actual injection dose}/\text{Prescribed injection dose})$$

5.9 Analysis of Immunogenicity Variable

Anti-A β antibodies will be summarized by presenting summary statistics of raw data and change from baseline values (n, mean, standard deviation, median, range) at each scheduled visit in mITT Population and PP Population.

The Kruskal-Wallis test or analysis of variance (ANOVA) for continuous variables for baseline information will be performed for comparing the un-adjusted change among Arm 1, Arm 2 and Arm 3.

A repeated-measures mixed-effects model with treatment (Arm 1+ Arm 2 vs. Arm 3, Arm 1 vs. Arm 3 and, Arm 2 vs. Arm 3), study visit, time-by-treatment, APOE4 status, and baseline as a

covariate will be used to analyze change from baseline of anti-A β antibodies. The unstructured covariance will be used in the modelling of the within-patient errors in the analysis. For APOE4 status subgroup analysis of MMRM, APOE4 factor will not be considered in the model. AUC of Anti-A β antibodies will be used an analysis of covariance (ANCOVA) model with treatment and baseline of Anti-A β antibodies as covariate. Antibody responders will be defined as the subjects with serum antibody titer > response threshold at any visit after baseline. The number and percentage of patients will be tabulated for each treatment group in mITT Population and PP Population at each post treatment scheduled visit. Treatment differences in the proportion antibody responders will be analyzed with the Chisq test. The one-sided 95% confidence interval (CI, right side) from all visits (V1 to V13) for subjects in Arm 3 (placebo group) will be calculated as the threshold of response.

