3 STUDY DESIGN

This is a 78-week, multicenter, randomized, double-blind, placebo-controlled Phase IIa study. Eligible subjects, 60 years or older with mild Alzheimer’s disease (AD), will be further screened by ¹⁸F-AV-45 PET scan for the presence of amyloid deposition.

Enrolled subjects will be randomized into one of the 3 treatment arms in 1:1:1 ratio. Subjects assigned to Arm 1 will receive 7 doses of UB-311 at Weeks 0, 4, 12, 24, 36, 48, and 60.

Subjects assigned to Arm 2 will receive 5 doses of UB-311 at Weeks 0, 4, 12, 36, and 60, and placebo at Weeks 24 and 48. Subjects assigned to Arm 3 will receive placebo at Weeks 0, 4, 12, 24, 36, 48, and 60. Subjects will be followed until Week 78. Subjects enrolled in the Phase I trial with UB-311 will be excluded from the Phase IIa trial.

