4 ANALYSIS VARIABLES

4.1 Demographic and Baseline Characteristics

The baseline value is defined as the last available value before the first injection of study drug. The following demographic and baseline disease characteristics will be summarized by treatment, by study center and overall for the randomized and treated population.

Demographic characteristics are defined as follows:

- Age (in years) to be derived as: (date of informed consent - date of birth)/365.25
- Gender (male/female)
- Body weight (kg)
- Body Mass Index (BMI, kg/m²): weight in kg/(height in meters)²
- Race

Disease characteristics including:

- Disease duration (years): (date of informed consent– date of diagnosis)/365.25
- APOE genotype
- Baseline scores of ADAS-Cog total score, MMSE total score, ADCS-ADL total score, CDR/CDR-SB total score, NPI total score

Inflammatory markers including:

- CRP
- ESR
- TNF- α
- IL-6
- IL-8

Physical examination, medical history and concomitant disease, previous and concomitant medication, and HIS score will be described at baseline.

The baseline safety data of clinical chemistry and hematology, inflammatory markers and number of microhemorrhages in the brain will also be summarized.

4.2 **Immunogenicity Variables**

The level of anti-A β antibodies is one of the primary endpoints and is assessed at baseline (V1) and every following visit (V2 to V13). The one-sided 95% confidence interval (CI, right side) from all visits (V1 to V13) for subjects in Arm 3 (placebo group) will be calculated as the threshold of response. Antibody responders will be defined as the subjects with serum antibody titer > response threshold at any visit after baseline.

Response rate, treatment difference and its 90% CI will be calculated.

The AUC of anti-A β antibodies will be served as exploratory endpoint. AUC will be calculated by the sum of individual trapezoid area under the curve of level of A β antibodies. In case of missing titer values, last observation carry forward will be used for AUC calculation.

4.3 **Efficacy Variables**

Efficacy variables are evaluated as secondary endpoints in this study.

The change from baseline in cognitive, functional, and global assessments through the end of the study

- Cognition: ADAS-Cog
 - The ADAS-cog 13 contains 13 items, with a total scoring range of 0 – 85 and higher scores indicating greater dysfunction.
- Cognition: MMSE

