5 STATISTICAL METHODS

5.1 General

Continuous data will be summarized by treatment group using the number of observations available (n), mean, standard deviation (SD), median, interquartile range (IQR), minimum, and maximum.

Categorical data will be summarized by treatment group using count and percentage. Missing data will not be categorized in the summaries.

In general, descriptive statistics of quantitative efficacy and safety parameters (results and changes from baseline) by scheduled visit will be provided on observed cases, i.e. the inclusion of only subjects with non-missing assessments at a specific visit.

For undetected value, this study will take the minimum value that can be detected as the text value, eg, <3.5 will be treated as 3.5 and <0.012 will be treated as 0.012 when performing the summary and will list the original value in listing.

- The pre-treatment period is defined as the time from the date of the informed consent to the time before the administration of first dose of study medication.
- The post-treatment period is defined as the time from after the first dose of study medication to the end of the study.

All statistical tests will be two-sided at the alpha level of 0.05, unless otherwise specified.

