5.11 Subgroup Analysis of Immunogenicity/Efficacy Data

Subgroup analysis by APOE4 carrier will be performed for all immunogenicity and efficacy data, and the analysis model will be the same as the overall analysis.

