Overall change from baseline for ARWMC frequency by visit will be summarized for safety population by treatment with number and percent of patients.

Visit value and Change from baseline for ARWMC will be summarized for safety population by treatment with n, mean, std dev, CV, Q1, median, Q3, Min, Max, L95 and U95.

Overall change from baseline for post- vaccine meningoencephalitis frequency by visit will be summarized for safety population by treatment with number and percent of patients.

5.13 **Sample Size**

This early phase clinical trial is exploratory in nature; hence, the sample size is determined to assess the primary objective of safety, tolerability, and immunogenicity of UB-311. The total of 45 subjects is planned to be enrolled, 15 per arms. For each UB-311-treated arm, 15 subjects are thought to be sufficient to detect an adverse event with an incidence of 7%. Furthermore, 30 subjects receiving UB-311 are anticipated to be able to detect an adverse event with an incidence of 4%.

With the current sample sizes, there may be limited power to detect a reduction in mean SUVRs or regional SUVRs unless there is a dramatic clearance of pre-existing plaques, and extremely limited power to detect effects on cognitive and functional endpoints. These analyses are therefore considered exploratory.

5.14 **Interim Analysis**

There is no interim analysis for this study.

5.15 **Multiplicity**

There is only primary immunogenicity endpoint in this study, and all efficacy endpoint will be served as secondary endpoint, and p-Value and its confidence interval will be used for screening purpose, so there is no multiplicity adjustment performed.

5.16 **General Conventions for Tables, Listings and Figures**

For summary tables, unless otherwise specified, the number of decimal places provided in the SAS output will be based on the accuracy of the least accurate value in the raw data as follows:

- n integer
- Arithmetic mean 1 decimal place more than the least accurate number in the raw data
- SD 2 decimal place more than the least accurate number in the raw data
- CV(%) 2 decimal places
- Geometric mean 1 decimal place more than the least accurate number in the raw data
- Median 1 decimal place more than the least accurate number in the raw data
- Minimum same number of decimal places as raw data

- Maximum same number of decimal places as raw data
- Confidence interval same number of decimals as the associated statistic

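### Refitting the 12-visit unstructured antibody model within each APOE4 stratum may give no fit, or standard errors that are too small, in the smaller stratum

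*SAP*

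**What the plan says.** Antibody level is part of the primary endpoint (SAP 2.3). It is measured at V1 and at each of V2 to V13 (SAP 4.2), which gives 12 post-baseline values per subject. SAP 5.9 analyses change from baseline with a repeated-measures model containing arm, visit, their interaction, APOE4 and baseline, and fixes the covariance: "The unstructured covariance will be used in the modelling of the within-patient errors in the analysis".

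The same section plans a version by APOE4: "For APOE4 status subgroup analysis of MMRM, APOE4 factor will not be considered in the model". SAP 5.11 extends the subgroup analysis to all immunogenicity and efficacy data and says that "the analysis model will be the same as the overall analysis". Read together, these two sections require the 12-visit unstructured model to be fitted separately in each APOE4 stratum. Immunogenicity is analysed in both the mITT and the per-protocol sets (SAP 5.3.1), so the requirement applies twice.

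On numbers, SAP 5.13 says: "The total of 45 subjects is planned to be enrolled, 15 per arms". SAP 5.3.3 states that the trial is not powered for subgroups and calls the APOE4 analyses exploratory. Neither document gives an APOE4 carrier share, a dropout rate, ML or REML for the antibody model, a degrees-of-freedom or small-sample method, or an alternative covariance if the unstructured fit fails.

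**The concern.** An unstructured matrix over 12 visits is demanding for 45 subjects and much more so for half of them or fewer. If the likelihood has no proper maximum in a stratum, the specified analysis cannot be produced. If it has one but few subjects support it, the estimated covariance is treated as known, and model-based standard errors come out too small.

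The SAP names no fallback, so a failed fit would lead to a structure picked after the data have been seen, and SAP section 1 would class that as unplanned. Separate fits also give no estimate of how far the vaccine effect differs between carriers and non-carriers, which is usually the reason for looking at such a subgroup.

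**Working it through.** **The plan's own figure.** There is none for this model. The only sample-size statement (SAP 5.13) concerns adverse events: 15 subjects for an incidence of 7% and 30 for 4%. The chance of at least one event is 1 − 0.93^15 = 66.3% and 1 − 0.96^30 = 70.6%. No probability level is stated, and the figures do not bear on this point.

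**Inputs from the documents.** 45 subjects, 15 per arm (SAP 5.13); three arms, 1:1:1 (SAP 3); 12 post-baseline visits (SAP 4.2); two-sided 0.05 (SAP 5.1).

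**Assumed inputs.** Carrier share 30–60%; monotone dropout of 0, 15 or 20% by Week 78; serial correlation 0.95 per 4 weeks, unless stated otherwise.

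**Step 1: parameters.**
- Covariance: 12 × 13 / 2 = 78.
- Fixed effects with APOE4 dropped: 3 arms × 12 visits + 1 baseline slope = 37.
- Total: 115. A stratum of 22 with complete data supplies 22 × 12 = 264 observations; a stratum of 16 supplies 192.
- The rating scales have three post-baseline visits (3 × 4 / 2 = 6 covariance parameters) and SUVR has two (3 parameters). The problem is confined to antibody.

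**Step 2: when a fit exists.** Removing three arm means at each visit leaves n − 3 independent residual vectors. The 12 visits and the baseline covariate must be linearly independent across them, so n − 3 ≥ 13, or n ≥ 16. With 15 or fewer subjects the likelihood is unbounded. Under monotone dropout the same condition falls on about 16 subjects still observed at Week 78.

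**Step 3: stratum sizes.** Whatever the carrier share, the smaller of two strata cannot exceed 22 of 45. At 30% carriers it is 0.30 × 45 = 13.5, about 14. At 60% the non-carriers are 0.40 × 45 = 18. The smaller stratum is thus 14–22 and the larger 23–31. With 15% dropout, the expected Week 78 completers are 18 × 0.85 = 15.3, 20 × 0.85 = 17.0 and 22 × 0.85 = 18.7. Per-protocol strata are smaller again.

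**Step 4: simulation of the specified model within a stratum.** 600 replicates per setting; uncorrected model-based standard errors; arm difference at Week 78. The entries are the percentage by which the mean standard error falls short of the true sampling SD (Monte Carlo error about 3 points).

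| Subjects | ML, complete | ML, 15% dropout | REML, complete | REML, 15% dropout | Singular fits, 15% dropout |
|---|---|---|---|---|---|
| 16 | 25 | 21 | 16 | 24 | 81–85% |
| 18 | 13 | 19 | 5 | 10 | 44–45% |
| 20 | 15 | 20 | 7 | 11 | 12% |
| 22 | 10 | 14 | 3 | 7 | 2% |
| 25 | 6 | 12 | 0 | 5 | 0 |
| 27 | 3 | 6 | 0 | 0 | 0 |
| 31 | 3 | 5 | 0 | 0 | 0 |
| 45 (whole trial) | 5 | 6 | 1 | 2 | 0 |

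With complete data, singular fits were at most 0.5%. At 18–20 subjects the rejection rate at nominal 5% (normal reference) was about 10–12% under ML and 7–9% under REML.

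A second run used 22 subjects, 20% dropout, and correlation 0.85 or 0.95 per 4 weeks (300 replicates per setting). Under ML the standard errors were 17–21% too small, rejection was 11%, and 12–16% of fits were near-singular. Under REML the figures were 10–14%, 8–9% and 11–13%. Expected completers there are 22 × 0.80 = 17.6, which helps explain why 22 subjects fare worse than in the table.

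**Step 5: one model on all subjects.** Treatment × visit × APOE4 with a common unstructured covariance has 3 × 2 × 12 + 1 = 73 fixed effects. The existence condition becomes n − 6 ≥ 13, or n ≥ 19, against about 36 completers at 20% dropout (45 × 0.80). In simulation with REML, APOE4-specific Week 78 standard errors were 2–3% too small, rejection was 6.7%, and no fit was near-singular.

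**The case against.** The strongest answer is that little rests on these fits. SAP 5.3.3 labels the subgroups exploratory and unpowered, SAP 5.13 describes the trial itself as exploratory, and SAP 5.15 applies no multiplicity adjustment. By-visit summaries, the AUC analysis and responder proportions need no 12 × 12 matrix, so a failed subgroup model loses one output among several. This stands, and it limits the consequence. It does not rescue the rule: exploratory status excuses low power, but not an interval that is too narrow or a specified model that may have no solution.

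SAP 5.3.3 also speaks of selected efficacy and safety endpoints, which could be read as leaving antibody out. SAP 5.9 and 5.11 both include it expressly, so that reading fails, though the wording should be aligned.

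A reader might infer that standard errors in APOE4 strata are generally 15–20% too small, or that there are about 7 subjects per arm in each stratum. The documents support neither. The first holds only for some combinations of stratum size, dropout and estimator; the second needs a carrier share near 50%, which is not given. Nor may the ML results be taken as what the plan specifies: maximum likelihood is named only in SAP 5.10, for the rating scales, and SAP 5.9 names no estimator. Uncorrected standard errors are likewise an assumption where the SAP is silent.

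Finally, the SAP promises no test of APOE4 interaction, so its absence alone is not an error.

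**Conclusion.** The concern holds for the smaller APOE4 stratum. That the stratum cannot exceed 22 of 45, and that no fit exists at 15 or fewer subjects, follows by arithmetic. Whether the stratum falls that low depends on the unknown carrier share; at 30% carriers it would. At 16–22 subjects, model-based standard errors are about 3–25% too small, and the risk of a singular fit runs from near zero with complete data to over 80% at 16 subjects with 15% dropout. These ranges rest on the assumed dropout, correlation and estimator, and on uncorrected standard errors; singular counts also depend on the cutoff used.

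The larger stratum is little affected: at 25–31 subjects the shortfall is 3–12% under ML and 0–5% under REML, with no singular fits. It would also be wrong to conclude that the primary antibody analysis is invalid. At 45 subjects the shortfall is 1–2% under REML and 5–6% under ML. The damage is limited to exploratory subgroup intervals and p-values, and to an unplanned choice of structure if the fit fails. The change is worth making because it is cheap and the specified rule performs worse than a simple alternative.

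**What to change.** In SAP 5.9 and 5.11, replace the separate antibody fits by one REML model on all subjects with treatment × visit × APOE4, baseline and a common unstructured covariance. Use Kenward-Roger standard errors and degrees of freedom. Report the arm contrasts within carriers and within non-carriers from this model, and the interaction as descriptive. State the estimator for the main antibody model as well.

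Prespecify what happens if the model does not converge. The fallback should respect the visit schedule: gaps alternate between 8 and 4 weeks from Week 4 to Week 64, then comes one of 14. AR(1) or Toeplitz by visit number assumes one correlation per lag, whereas 0.95 per 4 weeks implies 0.95, 0.90 and 0.84 across gaps of 4, 8 and 14 weeks. A spatial-power structure in weeks with heterogeneous variances is one suitable choice. Its standard errors need a small-sample correction; with 7 subjects in a cell, an uncorrected robust standard error is itself about 1 − √(6/7) = 7% too small.

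The cost is SAP wording and code, with no new data. The price is assuming that carriers and non-carriers share one covariance matrix.

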The dose selected for UB-311 is based on the data obtained from preclinical studies (Table 1). The anti-A $\beta$  antibodies were detected in sera of four of six Macaques after one immunization at the 150  $\mu$ g/dose level at 3 weeks post injection and six of six Macaques at the 750  $\mu$ g/dose level at 3 weeks post injection. The immunogenicity was also detected in sera of five of six baboons at the 300  $\mu$ g/dose level at 3 weeks post injection, and two of two baboons at the 1200  $\mu$ g/dose level at 3 weeks post injection. Therefore, the 300  $\mu$ g/dose was considered as an appropriate dose and the doses over 750  $\mu$ g were at the plateau of the optimal dose. Regarding the safety, no obvious adverse events occurred in the macaque groups receiving either 150 or 750  $\mu$ g/dose; only some site reactogenicity occurred in the group receiving the higher dose, 750  $\mu$ g/dose. Since human body weights are 10-fold to 20-fold higher than that of macaques, the safety associated with these doses will not be of concern. The 300  $\mu$ g/dose was selected as the dose for further clinical evaluation because it was found to be safe, well tolerated and strongly immunogenic as shown by all available preclinical evidences. In the Phase I clinical trial, UB-311 has demonstrated satisfying safety and tolerability profiles when administered to patients with clinically documented mild to moderate Alzheimer's disease (AD). It is also capable of eliciting antibodies with specificity to the N-terminus of the A $\beta$ 1-14 domain after administration by intramuscular route without causing any serious adverse events (SAEs) or intolerable adverse events (AEs). The response rate is 100%, using greater than one-sided 95% upper limit of the mean baseline titer as cutoff.

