5.10 Analysis of Efficacy Data

Efficacy analyses will be performed on the mITT and PP populations. For change from baseline of ADAS-Cog total score, MMSE total score, ADCS-ADL total score, CDR-SB total score, NPI total score, A repeated-measures mixed-effects model with treatment (Arm 1 + Arm 2 vs. Arm 3, Arm 1 vs. Arm 3 and , Arm 2 vs. Arm 3), study visit, time-by-treatment, APOE4 status, and baseline as a covariate will be used to analyze change from baseline. The least square means using maximum likelihood estimate and its 95% will be provided. The unstructured covariance will be used in the modeling of the within-patient errors in the analysis.

For change from baseline of mean SUVR, A repeated- measures mixed-effects model with treatment (Arm 1 + Arm 2 vs. Arm 3, Arm 1 vs. Arm 3 and, Arm 2 vs. Arm 3), study visit, time-by-treatment, APOE4 status, and baseline as a covariate will be used to analyze change from baseline. The unstructured covariance will be used in the modeling of the within-patient errors in the analysis.

For change from baseline of mean SUVR by region, A repeated- measures mixed-effects model with treatment (Arm 1 + Arm 2 vs. Arm 3, Arm 1 vs. Arm 3 and, Arm 2 vs. Arm 3), study visit, time-by-treatment, and baseline as a covariate will be used to analyze change from baseline. The unstructured covariance will be used in the modeling of the within-patient errors in the analysis.

The p-values and confidence intervals for these efficacy endpoints were not adjusted for multiplicity, it should be used for screening purposes only, and that one side of 95% confidence intervals are provided to help gauge the precision of the estimates for treatment difference.

The proportion of PET positive subjects with visual read will be provided by number and percentage for each treatment group in mITT Population and PP Population at each post treatment scheduled visit. Treatment differences will be analysed with the Chisq test. The one-sided 95% confidence interval (CI, right side) between (Arm 1 + Arm 2 vs. Arm 3, Arm 1 vs. Arm 3 and, Arm 2 vs. Arm 3) from all visits will be calculated.

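### Antibody response and PET visual read are assigned a chi-square test with no small-count alternative, although PET-conversion, APOE4-subgroup and possibly response tables will be sparse (minor)

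*SAP*

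**What the plan says.** SAP 5.9 (responders): "Treatment differences in the proportion antibody responders will be analyzed with the Chisq test". SAP 5.10 (PET visual read): "Treatment differences will be analysed with the Chisq test". Neither section states a continuity correction or a rule for small expected counts. By contrast, for baseline characteristics SAP 5.7.1 permits chi-square or Fisher's "exact test for categorical variables and the Kruskal-Wallis test or analysis of variance (ANOVA) for continuous variables".

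SAP 5.1 sets the level: "All statistical tests will be two-sided at the alpha level of 0.05, unless otherwise specified". SAP 5.13 gives the numbers: "The total of 45 subjects is planned to be enrolled, 15 per arms".

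For the PET interval, SAP 5.10 lists the contrasts "between (Arm 1 + Arm 2 vs. Arm 3, Arm 1 vs. Arm 3 and, Arm 2 vs. Arm 3". SAP 5.9 lists the same three for the mixed model but none for the responder test.

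A responder is a subject with "serum antibody titer > response threshold at any visit after baseline", where the threshold is derived from the placebo arm. SAP 4.2 adds a 90% CI for the response difference without naming a method. SAP 5.11 repeats all immunogenicity and efficacy analyses by APOE4 carrier status. SAP 5.15 reserves p-values for screening, without multiplicity adjustment.

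**The concern.** The chi-square p-value is a large-sample approximation, usually trusted when all expected counts are about 5 or more. Both endpoints may sit near a boundary. Inclusion criterion 15 makes every subject amyloid-positive at entry, so the PET test turns on the few who become negative. For response, Protocol section 1 reports from Phase I: "The response rate is 100%, using greater than one-sided 95% upper limit of the mean baseline titer as cutoff". If placebo responders are also common under the any-visit rule, non-responders will be few in every arm.

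At stake is a p-value below 0.05 on a component of a primary endpoint, or on a secondary endpoint, that an exact analysis would not support. The SAP already allows for sparse tables at baseline, where nothing depends on the result, but not for its endpoints.

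**Working it through.** **Inputs.** 15 per arm (SAP 5.13), so 15 v 15 for each regimen and 30 v 15 pooled; alpha 0.05 two-sided (SAP 5.1). Assumptions: uncorrected Pearson chi-square, full arms, and the three contrasts applied to both endpoints. The documents give no placebo response rate, PET conversion rate or APOE4 split, so ranges are used. The SAP has no figure of its own for these tests; its only sample-size figures concern adverse-event detection.

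**1. Expected counts.** If the rarer outcome totals t, the smallest expected count is 15t/45 = t/3 pooled and 15t/30 = t/2 per regimen. It is below 5 when t<15 or t<10 respectively.
- Response, clear effect: 30/30 v 0/15 gives 15/3 = 5.0; 30/30 v 1/15 gives 14/3 = 4.67; 15/15 v 1/15 gives 14/2 = 7.0. These are adequate, and both tests give p<0.0001.
- Response, many placebo responders: 30/30 v 7/15 gives 8/3 = 2.67; 30/30 v 13/15 gives 2/3 = 0.67.
- PET conversion: 7/30 v 0/15 gives 7/3 = 2.33; 4/15 v 0/15 gives 4/2 = 2.0.

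How common placebo responders might be depends on the threshold. If each of 12 post-baseline visits independently had a 5% chance of exceeding it, 1 − 0.95^12 = 46% would respond. A simulation with normal titres (assumed), 15 subjects and 13 visits gives 14% to 46% if the threshold is mean + 1.645 SD. If it is read as an upper limit for the mean, the figure is 67% to over 99%. In both cases the lower figure is for within-subject correlation 0.9 and the higher for 0.

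**2. Disagreement between tests (full enumeration).** Boschloo here is ordered by the two-sided Fisher p-value.

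| Table | Smallest expected | Chi-square | Fisher | Boschloo |
|---|---|---|---|---|
| 30/30 v 13/15 | 0.67 | 0.041 | 0.106 | 0.080 |
| 30/30 v 12/15 | 1.0 | 0.011 | 0.032 | 0.026 |
| 7/30 v 0/15 | 2.33 | 0.042 | 0.077 | 0.058 |
| 4/15 v 0/15 | 2.0 | 0.032 | 0.100 | 0.043 |

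Of the tables significant by chi-square, Fisher is not significant in 20 of 274 (30 v 15) and 24 of 126 (15 v 15). Half of each have a smallest expected count below 5. Against Boschloo the numbers are 10 of 274 and 4 of 126. Fisher is never significant where chi-square is not.

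The Boschloo convention matters. Doubling the one-sided value gives 0.123 for the first table and 0.045 for the third, so the third changes sides of 0.05.

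**3. Size.** For a common rate p, size is the sum of the two binomial probabilities over all rejected tables, maximised over p.

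| Test | 15 v 15 | 30 v 15 |
|---|---|---|
| Chi-square | 5.5% | 5.5% |
| Fisher | 1.8% | 3.3% |
| Boschloo | 4.3% | 4.9% |
| Fisher if any expected count <5, else chi-square | 4.3% | 4.7% |

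**4. Direction of error, pooled chi-square.** At a common response rate of 94.4% it favours UB-311 in 3.9% of trials and placebo in 0.05%. At 90% the split is 3.08% v 0.55%; at 80%, 2.73% v 2.26%; at 50%, 2.29% each. For a common PET conversion rate of 5.6% the split reverses: placebo converts more in 3.9%, UB-311 in 0.05%. At 15 v 15 the tails are always equal.

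**5. Subgroups.** At an assumed 8 v 8 the smallest expected count cannot exceed 8 × 8/16 = 4, and two-sided size reaches 7.7% (at a common rate of 50%). Over equal subgroups from 5 v 5 to 12 v 12 the maximum lies between 4.2% and 7.7%, so 8 v 8 is the worst case in that range.

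**The case against.** The strongest reply is that little depends on this. In the result the sponsor presumably expects for response, counts are adequate and every test agrees. With 30/30 active responders, chi-square and Fisher part company in the pooled test only at 13/15 on placebo. A placebo rate that high would point to a faulty response threshold, which no choice of test repairs. The SAP does not say whether the test is continuity-corrected; with Yates' correction no table is significant where Fisher is not. SAP 5.9 does not state that the pooled contrast applies to responders. P-values are for screening, and a CI is planned. All of this stands, and it makes the point minor.

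Three stronger readings are tempting, and the documents and figures do not support them:
- **That chi-square grossly inflates type I error.** Size at full numbers is at most 5.5%. At 15 v 15 with a common rate of 5% it is only 0.5%.
- **That the test is tilted towards UB-311.** That holds only for the pooled test at a high common response rate. With rare PET conversion the heavy tail goes against UB-311.
- **That an exact test removes the lopsidedness.** At a 94.4% common rate Fisher and Boschloo both give 1.14% v 0.008%. The heavy tail falls from 3.9% to below 2.5%, but the ratio between the tails is no smaller.

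What the reply does not meet is PET conversion and the subgroups. PET tables stay sparse unless at least 15 of 45 subjects (pooled) or 10 of 30 (per regimen) turn negative, and SAP 5.13 itself expects limited power on amyloid short of dramatic plaque clearance.

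**Conclusion.** The point holds as a minor gap in specification. The SAP names one large-sample test for two binary endpoints, with no fallback, in a trial where several of the planned tables will be sparse. The effect is isolated p-values on the wrong side of 0.05 (0.041 against 0.106 or 0.080; 0.042 against 0.077 or 0.058) and a pooled one-direction error of up to 3.9% near a boundary. It is not a general loss of error control.

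The figures rest on an uncorrected Pearson test, 15 evaluable subjects per arm, and the pooled contrast being applied to both endpoints. The 7.7% subgroup figure rests on an assumed 8 v 8 split. For response, the concern applies only if placebo responders are common or nearly everyone responds; the documents give no rate that settles this.

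**What to change.** In SAP 5.9 and 5.10, and through them in 5.11:
- State that the binary comparisons are Arm 1 + Arm 2 v Arm 3, Arm 1 v Arm 3 and Arm 2 v Arm 3, for responders as well as PET.
- Replace the chi-square with either Boschloo's exact unconditional test, with its two-sided convention stated (ordering by the two-sided Fisher p-value, or doubling), or a rule that Fisher's exact test is used when any expected count is below 5.
- Name the interval method for the difference: score-based (Miettinen-Nurminen) or exact.

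At full numbers this keeps two-sided error within 5% and lowers the heavy tail near the boundary; the asymmetry from 2:1 pooling remains. The cost is a few lines of SAP text and a small programming change. Some p-values become less favourable. Fisher used throughout is conservative (maximum size 1.8% at 15 v 15 and 3.3% at 30 v 15); Boschloo gives up less.
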